#### 3.2 Study devices and equipment

*Summary description:* The study device is a miniaturized implantable pulse generator with an integrated electrode lead. The pulse generator is powered by a primary (non-rechargeable) lithium cell. It can be programmed non-invasively by timed applications of an external magnet, or it can be programmed and interrogated non-invasively by external programmer model 9C-580.

[figure not shown]
Device manufacturer: Nine Continents Medical, Inc., [name].

Device identification: Model number 9C-680.

Device traceability: Each device has a unique serial number.

*Device purpose:* The pulse generator automatically provides stimulation at a pulse pattern and frequency preset to match those of percutaneous tibial nerve stimulation (PTNS), without requiring clinic visits for the patient to receive therapy.

*Materials in contact with tissues or body fluids:* Refer to the drawing below. The study device does not contain medicinal products, human or animal tissues or their derivatives, or other biologically active substances.

*Training and experience needed to use the device:* This is a prescription device for implantation by a physician. The investigator will complete study and device training before using the device.

*Medical or surgical procedures involved:* The miniaturized pulse generator is permanently implanted via a percutaneous procedure. The implant site is subcutaneous in the medial lower calf, distal to the gastrocnemius muscle. The electrode-lead integrated with the pulse generator is advanced distally from the same incision with a marketed implant kit. The study device provides electrical pulses to the posterior tibial nerve at a point approximately 5 centimeters proximal to the medial malleolus, which is the same location where PTNS is applied.

*Background for study:* Refer to sponsor's report of prior investigations R-00105 for a detailed list of verification and validation studies successfully completed for ITNS model 9C-680 and programmer model 9C-580. Briefly, ITNS validation studies included sterile packaging, sterilization, biocompatibility, and a six-month animal study with eight ITNS implanted in four sheep. ITNS verification studies included electromagnetic compatibility; electrical specifications, safety, and reliability; mechanical specifications, safety, and reliability; and device longevity and lithium cell integrity. Programmer verification studies included electromagnetic compatibility and electrical safety. ITNS and programmer software were validated. Risk analysis included system-level functions, RF wireless technology, and cybersecurity.

# 3.3 Subjects

*Point of enrollment:* The investigator will enroll study subjects at approved investigational sites after completing an investigator's agreement and receiving notification from the sponsor that the study has started.

*Concomitant medication:* Medication to be used during the study is at the investigator's discretion, however any change in medication with urinary effects or side effects after the screening visit must be recorded as a protocol deviation.

*Replacement of subjects:* This study has inclusion and exclusion criteria ( $\S$ 2.1 on page 3) intended to ensure that subjects complete the protocol after they receive the study device. Consequently this protocol has no provision for replacement of subjects after implantation.

*Efforts to minimize missed visits and drop-outs:* The sponsor or sponsor's designee will monitor the investigation as described in its established monitoring procedure and will promptly inform the investigator concerning missing data or missed visits. The investigator will remind subjects of scheduled visits by telephone or by E mail, and will document at least three (3) efforts to contact subjects who miss a visit (e.g. via registered mail, E mail, or telephone). If a patient cannot be contacted, this becomes a withdrawal or discontinuation.

*Incentives for subjects:* The investigator may provide special incentives to subjects for study compliance, but the compensation may not be so large as to unduly encourage the subjects to participate.

*Withdrawal or discontinuation:* A subject may withdraw from the study at any time, for any reason, and without stating a reason. Withdrawal or discontinuation will not prejudice a subject's future medical care by the investigation team or investigation site. Upon withdrawal or discontinuation a subject will have their ITNS explanted. An investigator may discontinue a subject's participation for any of the reasons below:

- Any unanticipated adverse device effect (see adverse event CRF) which is, in the opinion of the investigator, related to the treatment and will endanger the well-being of the patient if treatment is continued;
- Development of any concurrent illness, infection, or condition that might interfere with the investigation;
- Non-compliance with the clinical investigation procedures deemed by the investigator to be sufficient to cause discontinuation; or
- Any other problem deemed by the investigator to be sufficient to cause discontinuation.

*Follow-up care:* Subjects who do not qualify as responders at the 26-week visit will have their ITNS explanted. The investigator will provide medical care for the subjects after the clinical investigation has been completed, conforming to their standard practice.

# 3.4 **Procedure timing requirements**

**Informed consent** must be signed before a subject undergoes any test or procedure not required for routine care outside the study. For example, the following tests may be performed before signed informed consent, provided they are necessary for a patient's routine care: blood and urine analyses, physical examination, urodynamics, cystoscopy, and pre-therapy diary. The study device must never be used without prior signed informed consent. The investigator or an individual they designate must meet with each prospective subject to explain the study and alternatives before requesting consent.

The **pre-therapy diary** provides a baseline for calculating symptom improvement after implantation of the study device, consequently any improvement of OAB symptoms in the pretherapy diary due to prior therapy and medications could mask the effectiveness of the study device. Investigational sites may use the study's pre-therapy diary form for routine care outside the study. However, any pre-therapy diary used for the study must start:

- 1. At least 4 weeks after the most recent:
  - Use of any anti-muscarinics, beta-3 adrenergic agonists, or other OAB medications;
  - Dose change of any other medications with urinary side effects (e.g. Flomax, tricyclic antidepressants, diuretics); or
  - TENS use (back, pelvic, or legs).
- 2. After sufficient time for symptoms to return to baseline levels of after stopping PTNS or Botox for OAB. This time varies from subject to subject.

When completing the **pre-screening**, **screening**, and **pre-implantation** case report forms, the investigator may use results from tests performed for a patient's routine care outside the study, provided that the results are documented in the patient's medical record, and remain valid for the subject's current medical condition in the investigator's medical judgment. For example, this may include results from blood and urine analyses, physical examination, urodynamics, cystoscopy, and a pre-therapy diary as described above. Prior measurements of PTNS current required for motor response or sensation may be used.

From	То	Min weeks	Max weeks
Pre-screening evaluation	Screening visit	0	4
Informed consent	Screening visit	0	4
Screening visit	Pre-implantation evaluation	0	7
Pre-implantation evaluation	Implantation procedure	0	4
Implantation procedure	4-week follow-up visit	3	5
4-week follow-up visit	6-week follow-up visit	2	3
6-week follow-up visit	Daily therapy diary (optional)	0	2
6-week follow-up visit	19-week follow-up visit	12	14
19-week follow-up visit	Weekly therapy diary	0	2
Implantation procedure	26-week follow-up visit	25	27
26-week follow-up visit	Explantation (if non-responder)	0	4
Unplanned exit	Explantation (if implanted)	0	4

The table below provides additional procedure timing requirements:

#### 3.5 Adverse events and device deficiency definitions

The investigator will record and classify all adverse events and device deficiencies. They will record the onset and resolution times of each adverse event, noting the method of resolution. The investigator will record all adverse events and classify them as:

Device-related, procedure-related, or non-related.

- Serious or non-serious.
- Unanticipated adverse device effects or other.

An *adverse event* is any unfavorable medical occurrence, unintended disease or injury, or unfavorable clinical signs (including abnormal laboratory findings), in a subject, whether device-related, procedure-related, or non-related. It is also any such event, in a user or other person, if related to the study device.

A device-related adverse event is caused or contributed to by the study device. This definition includes adverse events involving insufficient or inadequate instructions for the study device, malfunction of the study device, or use error or intentional misuse of the study device.

A procedure-related adverse event is caused or contributed to by a procedure required to use the study device.

Because of the difficulty of determining the root cause of genitourinary events, the investigator will categorize events conservatively as either device- or procedure-related unless there is clear evidence of other causation.

A *serious* adverse event is one that either:

- a) Led to death, or
- b) Led to serious deterioration in the health of the subject, that either resulted in:
  - 1) A life-threatening illness or injury, or
  - 2) A permanent impairment of a body structure or a body function, or
  - 3) In-patient or prolonged hospitalization, or
  - 4) Medical or surgical intervention to prevent life-threatening illness or injury or permanent impairment to a body structure or a body function.

Planned hospitalization for a pre-existing condition, or a procedure required by the investigational plan, without serious deterioration in health, is not considered a serious adverse event.

An *unanticipated adverse device effect* (UADE) is a serious adverse event that is device- or procedure-related, and is not identified in the protocol by its nature, incidence, severity, or outcome. The table below identifies potential serious adverse device effects:

Nature	Incidence	Severity	Outcome
Implant-procedure related complication: infection; damage to nerves, tissues, or vessels; migration; erosion or extrusion; pain at implant site.	< 40%, based on initial clinical experience of SNS	Serious	Surgical revision including explant; intent- to-treat failure.
Increase in the pulse amplitude required for neuromodulation, beyond the range of the pulse generator.	< 15 % (one event maximum in an early feasibility trial)	Serious	Surgical revision and/or loss of significant device function.
Study device malfunction causing or contributing to failure to deliver neuromodulation therapy.	< 15 % (one event maximum in an early feasibility trial)	Serious	Surgical revision and/or loss of significant device function.

Initial clinical experience of SNS: SNS studies reported frequent adverse events, including pain at the stimulator site (3.3 to 19.8% of patients), pain at the lead site (4.5 to 19.1% of patients), lead migration (2.2 to 8.6% of patients), infection/irritation (2.2 to 14.30% of patients), electric shock (5.5 to 10.2 7.9% of patients) and need for surgical revision (6.25 to 39.5% of patients). In most studies, the need for surgical revision occurred in greater than 30% of patients (Gormley, et al., 2014).

The investigator will report all device deficiencies involving the study device, whether or not they involve adverse events. A *device deficiency* is an inadequacy of a medical device with respect to its identity, quality, durability, reliability, safety or performance. This includes malfunctions, use errors, and inadequate labeling.

*Timing:* The investigator will report serious adverse events to the sponsor and IRB within 24 hours. They will report other adverse events and device deficiencies to the sponsor within 30 days.

#### 3.6 Activities performed by sponsor

The investigator will perform or supervise all required study procedures. The sponsor's personnel may assist at study device implant, assessment of adverse events and device deficiencies, and measurement of response threshold.

#### 3.7 Investigator selection and training

The sponsor will select a study site and investigator capable of recruiting sufficient numbers of eligible subjects, representative of the target population for the study device.

To help ensure the safe, proper, and consistent use of the investigational device, the sponsor will conduct a training program to educate investigators and their staff on the use of the study device. This training will consist of didactic instruction, covering the device functions and principles of operation. Additionally, the training will highlight the important or unique aspects of the clinical study, such as screening, obtaining informed consent, the follow-up schedule, data collection methods, and adverse event reporting. Finally, the training will include a cadaver study.

#### 4 Data management

#### 4.1 Case report forms (CRFs)

Refer to §3.1 on page 6.

# 4.2 Procedures used for data review, database cleaning, and issuing and resolving data queries

The sponsor will enter all CRF data into a central database. The sponsor will review all incoming data to identify inconsistent or missing data as well as any adverse events. The sponsor will promptly address any data issues with the investigator.

# 4.3 Procedures for verification, validation and securing of electronic clinical data systems, if applicable.

This clinical investigation will use paper CRFs rather than an electronic clinical data system.

#### 4.4 Procedures for data retention and specified retention period

The sponsor and investigator will maintain the clinical investigation documents for a minimal period of five (5) years after the clinical investigation is completed, or longer depending on national requirements. They will take measures to prevent accidental or premature destruction of these documents and ensure these are filed in a secure place. Investigator or sponsor may transfer custody of records to another person or party and document the transfer at the investigation site, or at the sponsor's facility.

The investigator will maintain all source documents required by the protocol, including laboratory results, supporting medical records, and signed informed consent forms.

#### 4.5 Other aspects of clinical quality assurance, as appropriate

The measures described in §4.1 through §4.4 provide appropriate clinical quality assurance for an early feasibility study.

# 4.6 Study report

The sponsor will provide a study report with tables listed below. Each table will provides data organized by subject unless otherwise noted.

Table	Information provided		
Study summary	Investigational plan title and version; IDE number and approval date; clinical investigation suspension and/or completion dates.		
Sites	Site number, name, and address; investigator names; IRB name and approval date; number of subjects consented and number of subjects implanted at the site.		
Subject demographics	Age, sex, race, and ethnicity. (NIH recommends collecting race and ethnicity).		
Subject accountability	Date completed for each procedure required by the protocol, with total number of subjects that complete each procedure (CONSORT diagram data).		
Medications	Type, dose, and dose interval for any medications with urinary effects or side effects.		
Procedure timing	Compliance with protocol requirements for minimum and maximum time between procedures.		
Unplanned exits	Any exits for withdrawal of consent, death, or loss to follow-up.		
Protocol deviations	Type of deviation, reason for deviation, description of deviation, and effect of deviation (management of potential adverse effects on rights, safety, or welfare of subject and/or scientific soundness of the study).		
Adverse events	Dates of onset and resolution, seriousness, relatedness, and description of adverse event.		
Device deficiencies	Date of onset, type and description of device deficiency.		
Thresholds	Lowest amplitudes at which paresthesia or motor response occurred, at screening visit; implantation; and 4-, 6-, 19-, and 26-week follow-up visits.		
Durations	Time from implantation procedure start to end, and time from implantation procedure end to discharge.		
Pre-therapy diary	Average events per 24 hours: incontinence, frequency, nocturia, and urgency. Whether or not subject met each of the 4 inclusion criteria.		
First therapy diary	Average events per 24 hours: incontinence, frequency, nocturia, and urgency. Improvement or worsening from baseline after 2 weeks of daily therapy.		

Table	Information provided	
Second therapy diary	Average events per 24 hours: incontinence, frequency, nocturia, and urgency. Improvement or worsening from baseline after 13 weeks of weekly therapy.	
Quality of life	From pre-therapy, first therapy, and second therapy diaries: OAB-q Part A and Part B scores and GRA scores, with changes from baseline.	
Device accountability	For each ITNS released for investigational use: delivery site and date; implant attempt subject #, date, and outcome; explantation reason and date; return reason and date; and returned product analysis result and date.	

The report will include descriptive statistics (average and standard deviation) for all effectiveness endpoints, and will employ graphical displays such as spaghetti plots to represent individual changes.

### 5 Rationales for endpoints

*Safety endpoints:* The adverse event endpoint in this study comes from FDA guidance (FDA, 2011-03-08) and is often used in medical-device studies. The neuromodulation pulse amplitude endpoint comes from the sponsor and is intended to detect functional changes in the interface between the stimulation electrode and the biological substrate it stimulates, analogous to pacing thresholds measured in studies of cardiac electrode-leads.

*Effectiveness endpoints:* OAB is a symptom complex with four factors: incontinence, frequency, nocturia, and urgency. For incontinence, objective endpoints for improvement and cure come from FDA guidance (FDA, 2011-03-08). For the other OAB factors, objective endpoints for improvement are similarly defined as a 50 % reduction in pathological episodes: frequency (voids during waking hours exceeding 7), nocturia (voids awakening from sleep), and urgency (voids with moderate to severe urgency). Subjective endpoints (quality of life) are a questionnaire selected for OAB symptoms including urinary incontinence and a global response assessment (Peters, et al., 2010).

#### 5.1 Rationale for the criterion for improvement in frequency

Frequency improvement is defined as a 50 % reduction from baseline of the number of voids during waking hours exceeding 7. This criterion takes into account that traditionally up to 7 micturition episodes during waking hours has been considered normal (Fitzgerald & Brubaker, 2003). This criterion is analogous to the criteria for improvement for the other three OAB components (incontinence, nocturia, and urgency), all of which require a 50 % improvement in the number of pathological events. Seven or fewer daytime voids are not pathological. A 50 % improvement in daytime voids exceeding 7 is a 50 % improvement in pathological events. This same endpoint (50 % improvement in frequency exceeding normal) is currently used in an IDE trial for another OAB device, NCT02873312 on clinicaltrials.gov.

# 5.2 Rationale for the criterion for worsening

# Background:

• In pre-IDE Q161967 the sponsor proposed defining a responder as a subject with significant improvement of at least one OAB symptom (e.g. 50 % better). FDA provided feedback: "Patients would be considered 'responders' if they improve significantly by one of those criteria but are overall worse in terms of their overactive bladder (OAB) symptoms. Criteria

for 'responder' should depend upon the underlying diagnosis/diagnoses and require that the patient meet the elements for all relevant diagnosis." The sponsor was concerned that this required a subject to demonstrate significant improvement for every relevant symptom to qualify as a responder, even though improvement in a single symptom could have clinical significance.

Therefore in Q161967/S001 the sponsor proposed defining a responder as a subject with significant improvement of at least one symptom and no significant worsening of any other symptom (e.g. 50 % worse). FDA provided feedback again: "Worsening of incontinence episodes and the number of voids would be any increase over the respective baseline number. A threshold of a 50% increase in order to be counted as worsening is arbitrary and lacks clinical meaning." The sponsor was concerned that with this definition, a vanishingly small worsening of one symptom could classify a subject as a non-responder, despite a significant improvement of one or more other symptoms.

To address FDA's and sponsor's concerns, this protocol defines a responder as a subject demonstrating significant improvement of at least one relevant OAB symptom (e.g. 50 % better), and no worsening of their relevant symptoms overall (worsening would be any increase overall). Here "relevant" means meeting the inclusion criterion for a symptom at baseline, and "overall" means average of changes over all relevant symptoms.

For example, a subject with a baseline diary showing daily averages of 9 voids during waking hours, 3 interrupting sleep, 5 with urgency, and 0.3 with incontinence would meet the study's inclusion criteria in §2.1 for nocturia and urgency (i.e. the subject would have two relevant symptoms). If their therapy diary showed daily averages of 1 void interrupting sleep and 6 with urgency, that would correspond to a -67 % change (improvement) in nocturia but a +20 % change (worsening) in urgency, or an overall change of -44% (improvement). That subject would qualify as a responder.

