#### 2.3 Endpoints

A clinical feasibility study is a clinical investigation that is commonly used to capture preliminary safety and effectiveness information on a near-final or final device design to adequately plan an appropriate pivotal study (FDA, 2013-10-01). A feasibility study does not collect definitive evidence; consequently it does not require statistical hypotheses or classifying objectives and endpoints as primary or secondary.

Section s on page 15 provides rationales for endpoints.					
Type of endpoints	List of endpoints				
Safety	Incidence, severity, and relatedness of all adverse events and device deficiencies.				
	Stability of neuromodulation pulse amplitude required to evoke paresthesia or muscle response ("threshold").				

Section 5 on page 15 provides rationales for endpoints.

Type of endpoints	List of endpoints		
Effectiveness, OAB symptoms	Incontinence: Improvement = $50 \%$ reduction from baseline of number of episodes. Dryness = 0 episodes.		
Averages per 24 hours, measured with 3-day voiding diaries	Frequency: Improvement = 50 % reduction from baseline of voids during waking hours exceeding 7. Cure = number of voids during waking hours $\leq$ 7 (note: FDA uses the term "cure" to describe normal frequency).		
	Nocturia: Improvement = $50\%$ reduction from baseline of number of voids interrupting sleep.		
	Urgency: Improvement = $50\%$ reduction from baseline of number of voids self-reported with moderate to severe urgency.		
Effectiveness, responder criterion	Subject demonstrating 50 % reduction in at least one relevant OAB symptom above and no worsening of their relevant symptoms overall. Here "relevant" means meeting the inclusion criterion for a symptom at baseline, and "overall" means average of percentage changes over all relevant symptoms.		
Effectiveness, quality of life	OAB-q, short form symptom bother (Coyne, Matza, & Thompson, 2005).		
	GRA, global response assessment (Propert, et al., 2006).		

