#### 3 Methods for assessing and recording variables

#### 3.1 Procedures

The study will include procedures listed below and will document results with standardized case report forms (CRFs). Refer to designated forms for detailed instructions for each procedure, and refer to  $\S3.4$  for procedure timing requirements.

Procedure	Form #	Purpose		
Pre- screening evaluation	D-00288	Preliminary assessment of medical records for inclusion and exclusion criteria for potential subject.		
Informed consent	R-00108	Documentation of potential subject's informed consent, required for enrollment in the study and participation in procedures required specifically for the study.		
Screening visit	D-00290	Record of demographics. Confirmation of inclusion and exclusion criteria though subject interview; physical examination; urodynamics, cystoscopy, urinalysis, and pregnancy tests (subjects without documented urodynamics and cystoscopy results prior to screening will be required to undergo these tests before completion of the screening visit).		

Procedure	Form #	Purpose		
Pre-therapy diary	D-00291	3-day voiding diary to assess baseline incontinence, frequency, nocturia, and urgency. OAB-q SF for quality of life (QOL). Subjects may optionally continue the diary for up to 7 days total. Subjects who cannot or will not complete a diary will exit the study.		
Pre- implantation evaluation	D-00292	Assessment of routine blood chemistry, and OAB symptom severity from pre-therapy diary, to qualify or disqualify subject for device implantation.		
Implantation procedure	D-00293	Implantation of ITNS per IFU. Threshold assessment with external device and ITNS. ITNS therapy programmed off for a 4- week healing period.		
4-week follow-up visit	D-00294	Threshold assessment with ITNS for changes since implantation. ITNS programmed to threshold amplitude and daily therapy (for potentially reducing time to therapy effect).		
6-week follow-up visit	D-00295	Threshold assessment with ITNS for changes after two weeks of daily ITNS therapy. ITNS programmed to threshold amplitude and weekly therapy (to preserve device longevity).		
Daily therapy diary (optional)	D-00296	3-day voiding diary to assess changes from baseline OAB symptoms after 2 weeks of daily ITNS therapy. OAB-q and GRA to assess QOL changes. Subjects may optionally continue the diary for up to 7 days total.		

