19-week follow-up visit	D-00297	Threshold assessment with ITNS for changes after 13 weeks of weekly ITNS therapy. ITNS programmed to threshold amplitude and weekly therapy.		
Weekly therapy diary	D-00298	3-day voiding diary to assess changes from baseline OAB symptoms after 13 weeks of weekly ITNS therapy. OAB-q and GRA to assess QOL changes. Subjects may optionally complete a second weekly therapy diary at 26 weeks after implantation. Subjects may optionally continue each diary for up to 7 days total.		
26-week follow-up visit	D-00299	Final safety assessment 26 weeks after implantation. Non- responders (as assessed with the latest weekly therapy diary) require device explantation; responders continue with site's standard of care.		
Explantation procedure	D-00300	Explantation of ITNS for any subject with an unplanned exit during the study or for a non-responder after 26 weeks of implantation.		
Adverse event	D-00301	Assessment of nature, onset, actions taken, outcome, relatedness, and seriousness for any unfavorable medical occurrence, including patient complaints.		

Procedure	Form #	Purpose
Device deficiency	D-00302	Record of nature, onset, and actions taken for any device malfunction, use error, or inadequate labeling.
Unplanned exit	D-00303	Record of any exit from the study due to withdrawal of consent, death, or loss to follow-up (including date and type of three attempts to contact the subject). Withdrawal of consent for dissatisfaction with device or procedure also requires an adverse event form.
Protocol deviation	D-00304	Description of type and reason for any protocol deviation, where a required item was not performed, performed early or late, or performed not according to protocol.

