# 5.3 Dichotomous and continuous criteria

This study requires a dichotomous "responder" criterion for an individual subject, to inform a decision about allowing the subject to keep the study device after the 26-week follow-up visit. As discussed above, FDA guidance also recommends dichotomous "improvement" criteria for individual subjects, e.g. 50 % symptom improvement.

As a feasibility study, this protocol does not establish prospective criteria for effectiveness for all subjects as a group. A pivotal study would establish hypothesis testing for statistics such as percentages of subjects meeting a dichotomous criterion, and averages over subjects of a continuous parameter. To inform the design of the pivotal study, this feasibility study will report descriptive statistics (including average, median, minimum, maximum, and standard deviation) for all effectiveness endpoints, and will employ graphical displays such as spaghetti plots to represent individual changes.

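### Does the -44% in the worked responder example, where the stated rule gives about -23%, put responder classification at risk?

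*Combined protocol and SAP*

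**What the plan says.** Section 2.3 (Endpoints) sets two conditions for a responder: a 50% reduction in at least one relevant symptom, and no worsening of the relevant symptoms overall. A symptom is relevant if it met its inclusion threshold at baseline, and overall "means average of percentage changes over all relevant symptoms". Section 5.2 repeats the definition slightly more loosely: overall "means average of changes over all relevant symptoms". It adds that any overall increase counts as worsening.

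Section 5.2 then gives the document's only worked calculation of the rule. The subject has two relevant symptoms. Nocturia goes from 3 to 1 per day, printed as -67%. Urgency goes from 5 to 6, and the example gives "a +20 % change (worsening) in urgency, or an overall change of -44% (improvement"). It concludes that the subject is a responder.

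Responder status has a consequence for the individual. Section 3.3 states: "Subjects who do not qualify as responders at the 26-week visit will have their ITNS explanted". Section 5.3 says that the criterion is needed "to inform a decision about allowing the subject to keep the study device after the 26-week follow-up visit".

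**The concern.** The printed total does not follow from the two changes printed beside it. One symptom improved by about two thirds and the other worsened by a fifth, so the average should lie well short of -44%. The mistake falls on the one step the example exists to show: how a worsening offsets an improvement.

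An obvious candidate for the cause is a lost sign, with the 20% worsening added to the improvement instead of set against it. If responder status were calculated that way, every change would count as improvement and the condition against overall worsening could never fail. Section 5.2 shows that this condition was written to answer the regulator's objection that a subject who is worse overall could still be called a responder. With 10 implanted subjects and device retention depending on the result, even one misclassification would matter.

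**Working it through.** **Inputs.** The Section 5.2 example gives baseline daily averages of 9 waking voids, 3 voids interrupting sleep, 5 with urgency and 0.3 incontinence episodes. On therapy there is 1 void interrupting sleep and 6 with urgency. The Section 2.1 thresholds are 11, 2.0, 4 and 1 respectively, so only nocturia (3 against 2.0) and urgency (5 against 4) are relevant. The example says the same.

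**Component changes.**
- Nocturia: (1 - 3)/3 = -66.7%, printed as -67%.
- Urgency: (6 - 5)/5 = +20%, as printed.

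Both reproduce.

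**Overall change under the Section 2.3 rule.**
- From the counts: (-66.7 + 20)/2 = -23.3%.
- From the printed percentages: (-67 + 20)/2 = -23.5%.

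The printed -44% does not reproduce. With nocturia at -66.7%, an average of -44% would need an urgency change of 2 × (-44) + 66.7 = -21.3%, a fall from 5 to about 3.9. The example has a rise to 6.

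**Other readings of the average.**
- Raw counts: (-2 + 1)/2 = -0.5 per day, which is not a percentage.
- Pooled counts: (7 - 8)/8 = -12.5%.
- Sum instead of mean: -66.7 + 20 = -46.7%.
- Geometric mean of the ratios: √((1/3) × (6/5)) - 1 = -36.8%.

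None gives -44%.

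**Possible sources of the slip.**
- Sign lost: (-67 - 20)/2 = -43.5%, which rounds to -44%. From unrounded inputs it is -43.3%.
- Digit misprinted: -23.5% rounds to -24%, one digit away from -44%.

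The documents do not settle which occurred.

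**Effect on the example.** Nocturia fell by 66.7%, which meets the 50% condition. The overall change is below zero at either -23.3% or -44%. The subject is a responder in both cases.

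**When the worsening condition can fail.** At least one relevant symptom must already have fallen by 50% or more. The average is then positive only if the percentage changes in the other relevant symptoms sum to more than +50%. With one relevant symptom this cannot happen. With two, the other must worsen by more than 50%. In the example it must worsen by more than 66.7%, to above 5 × 1.667 = 8.3 per day.

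**Size of the feared error.** Take nocturia 3 to 1 and urgency 5 to 9 (+80%). The rule gives (-66.7 + 80)/2 = +6.7%, a non-responder. With the sign lost it would be (-66.7 - 80)/2 = -73.3%, a responder. A sign-blind calculation would therefore change the result, but only for a subject with a marked worsening in one symptom alongside a large improvement in another.

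**The case for a change.** The best case for acting is that this is the sole worked example of a rule that bears on whether a subject keeps an implanted device, that it goes wrong at the offsetting step, and that correcting it costs almost nothing. Section 7 also says that the pivotal study will use the same procedures and endpoints if this study goes as planned, so the mistake could be carried forward. Section 5.2 leaves out the word percentage, which Section 2.3 includes.

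The arithmetic part stands: -44% is wrong and about -23% is right. The consequence does not follow. The lost sign is only one possible cause; if a digit was misprinted, there is no faulty method to copy. A reader who takes the example as a template sees the +20% marked as a worsening and the -67% marked as an improvement, just after being told that any overall increase is worsening. To treat the +20% as a gain, that reader would have to disregard all of this.

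The example sits in a rationale section, while the definition is in Section 2.3. For conduct of the procedures, Section 3.1 tells staff: "Refer to designated forms for detailed instructions for each procedure". Those forms are not among the documents, and nothing suggests that they repeat the misprint. The missing word is supplied by Section 2.3 and by the percentages in the example itself.

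A related question is which base the frequency term takes in the average. Section 5.1 answers it for improvement: "Frequency improvement is defined as a 50 % reduction from baseline of the number of voids during waking hours exceeding 7". An analyst would naturally carry that base into the average. The misprint does not bear on it, since 9 waking voids is below the threshold of 11 and frequency does not enter the example.

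**Conclusion.** The printed figure is an arithmetic or typing slip of about 20 percentage points (-44% against -23.3%), with no effect on classification, rule, design or reporting. The rule uses only whether the average is an increase. The size of the average is neither an endpoint in Section 2.3 nor a listed item in the report tables of Section 4.6. The study tests no hypothesis and sets no effectiveness criterion for the group, so no inference depends on it.

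This rests on one assumption: that whoever calculates responder status applies the Section 2.3 definition with the signs the example prints. The documents support that reading and show no misclassification. The number can be tidied as an erratum whenever the document is next reissued, but nothing that the trial does or concludes would change.
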